1.0 STUDY PURPOSES AND OBJECTIVES

This study is designed to obtain positron emission tomography with x-ray computed tomography (PET/CT) scan data according to the Specific Aims of Small Business Innovation Research (SBIR) grant 2R44CA257522 from the National Cancer Institute (PI=[name]; consortium between MultiFunctional Imaging LLC and HCI). PET/CT exams will be acquired for three pairs of radiopharmaceuticals: FDG + Cu64-DOTATATE and FDG + Ga68-DOTATATE in patients with known or suspected neuroendocrine tumors; and FDG + Ga68-PSMA-11 in patients with known or suspected prostate cancer. All of these radiopharmaceuticals are FDA approved, and each radiopharmaceutical will be used according to its approved indications for use. The study data will be used by the sponsor company, MultiFunctional Imaging LLC (MFI) according to the aims of the grant to develop new techniques and algorithms for simultaneous dual-tracer PET imaging of these tracer pairs. **The overall objective is to obtain scan data for developing new techniques and algorithms for simultaneous dual-tracer imaging of these tracer pairs with PET.**

The PET scans will be acquired using specially-designed “multi-timepoint” scanning sequences that acquire more images than would be obtained in routine standard of care PET/CT scans. The study will be performed over three Arms. Each Arm will acquire separate, single-tracer scans of two tracers on separate days in each subject, and the 2nd tracer used for each Arm will differ as follows:

- Arm 1 = FDG and Cu64-DOTATATE PET/CT exams in 15 subjects with known or suspected neuroendocrine tumors (NETs);
- Arm 2 = FDG and Ga68-DOTATATE PET/CT exams in 15 subjects with known or suspected NETs; and
- Arm 3 = FDG and Ga68-PSMA PET/CT exams in 20 subjects with known or suspected prostate cancer with suspected metastasis or recurrence.

The PET/CT exams will be acquired at HCI, and the visual and semi-quantitative image assessments described in Section 5.0 will also be performed at HCI. The resulting images and assessment results will be de-identified and delivered to MFI, where the images will be analyzed and used for the Specific Aims of the research grant, including the analyses described in Section 6.0. Here, the separate-scan images obtained in each Arm will be combined to “synthesize” corresponding simultaneous dual-tracer images—enabling development and testing of various simultaneous dual-tracer processing algorithms, where the original single-tracer images provide “gold standard” references for recovering individual-tracer images from the combined dual-tracer ones. This is a well-established approach for developing rapid dual-tracer PET techniques [1-13], and in essence it allows for the data to act as their own controls.

This study is funded by National Cancer Institute grant 2R44CA257522, and it will be performed as part of a consortium agreement between MFI and the University of Utah under that grant. The overall goal is to develop techniques and algorithms for simultaneous dual-tracer imaging of these tracer pairs. This requires sets of dual-tracer PET data acquired using specially-designed multi-timepoint acquisition protocols that facilitate the development and study of simultaneous

dual-tracer PET imaging techniques. New algorithms for processing dual-tracer PET images will be developed and tested using these data. These algorithms are not part of any medical device, and the approach of using multi-timepoint dual-tracer PET scanning is novel and requires the development of new algorithms to process these data and recover individual-tracer PET images.

It is important to note that the primary goal is to develop new technologies, *not* to investigate the clinical value of the PET tracers being used. Indeed, all four PET tracers are FDA approved and will be used within their approved indications for use. Also note that this study is *not* an NIH-defined clinical trial. This distinction is clearly identified in the R44 grant application (PHS Human Subjects section; Clinical Trial Questionnaire: the study is *not* “designed to evaluate the effect of the intervention on the participants” and does *not* “evaluate a health-related biomedical outcome”). *I.e.*, the study is *not* designed to evaluate the efficacy of the PET tracers being used. Instead, the study is designed to develop new dual-tracer PET imaging techniques and evaluate whether or not individual-tracer PET images can be recovered from simultaneous dual-tracer PET scans.

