2.0 BACKGROUND

2.1. Dual-Tracer PET Technologies and MFI

MultiFunctional Imaging LLC (MFI) is a University of Utah spinoff company that is investigating technologies patented at the University for rapidly imaging multiple PET tracers in a single scan. Under research grant 2R44CA257522, MFI is investigating novel techniques for simultaneously imaging several tracer pairs. These include simultaneous imaging of FDG + Cu64-DOTATATE and FDG+ Ga68-DOTATATE for NETs, and of FDG + Ga68-PSMA for prostate cancer. The rationale for imaging these tracer combinations is provided below. The proof-of-concept for the new simultaneous dual-tracer PET techniques was established under a previous Phase I grant. The current Phase II grant will study the new simultaneous dual-tracer PET techniques in depth,

develop new algorithms for processing simultaneous dual-tracer PET images, and evaluate how well these algorithms can recover individual-tracer images from simultaneous dual-tracer PET datasets.

The clinical research study described by this protocol is designed to obtain dual-tracer PET/CT imaging data with each tracer pair according to the Specific Aims of the grant, providing the imaging data needed to develop new simultaneous dual-tracer imaging techniques and processing algorithms for these tracer pairs. The study design uses established physics/engineering principles, and it is based on two decades of research and development in dual-tracer PET by the investigators.

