5.2. Semi-Quantitative Assessments

Tracer uptake in each lesion identified in the qualitative visual analysis will be quantified by calculating body-weight-corrected Standardized Uptake Values (SUV_{bw}) as follows:

$$SUV_{max} = \frac{A_{max}}{\text{injected activity (mCi)} / \overline{BW}}$$

where $\overline{A_{max}}$ = radioactive concentration (mCi/mL)

\overline{BW} = body weight BW (g)

Corrections for lean body mass will also be performed to calculate the SUV_{lean} as follows:

$$\text{SUV}_{\text{lean}} = (\text{LBM}/\text{BW}) \times \text{SUV}_{\text{bw}}$$

where SUV_{bw} = the SUV measurements using body-weight corrections

LBM = the lean body mass estimated from the Janhasastian Formula [98]

A region-of-interest (ROI) will be drawn over the lesions (on all image slices with abnormal uptake). The mean value in each ROI will be computed to obtain the SUV_{mean} for each tracer, and the maximum value in each ROI will be computed to obtain the SUV_{max} for each tracer.

The location, ROI, SUV_{mean}, and SUV_{max} for each lesion will be recorded and used for data analysis.

6.0 **DATA ANALYSIS AND STATISTICS**

The de-identified images with marked lesion locations will be provided to MFI for further analysis according to the aims of grant 2R44CA257522. The imaging data will be used to develop dual-tracer PET scanning protocols and new processing algorithms for imaging FDG + Cu64-DOTATATE, FDG + Ga68-DOTATE, and FDG + Ga68-PSMA-11. Since a dual-tracer PET image is essentially the sum of two single-tracer PET images, this research will make use of the synthesized dual-tracer evaluation technique summarized below.

6.1. **Synthesized Dual-Tracer Evaluation Technique**

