One challenge of evaluating rapid multi-tracer PET techniques is the need to know the ground truth when evaluating results. For example, one possible study design would be to obtain separate, single-tracer scans with each tracer on separate days, and then to obtain simultaneous dual-tracer scans on a 3rd day—all in the same patient. Here the separate-scan images of each tracer could be used as the standard for evaluating images of each tracer recovered from the dual-tracer scans. However, such an approach would pose many problems, in particular: (1) high cost, scheduling challenges, and patient compliance issues for performing 3 different PET/CT exams on 3 different days; (2) increased radiation exposure from 3 PET/CT exams (3 CTs and 4 total PET tracer administrations); (3) test-retest variability for PET is on the order of 10-15% [99-101]—differences that can be larger than the errors in recovered dual-tracer images and thus limit the value of the study; and (4) it would only allow for a single dual-tracer scanning protocol to be studied (rather than allowing for various scanning protocols to be studied and compared).

A better and widely-accepted approach, used by our group and others [2-8, 10-13] is to acquire separate, single-tracer PET scans with each tracer and then retroactively combine the images to “synthesize” dual-tracer images which are ~identical to the images that would have been obtained from actual dual-tracer scanning. When more than one PET tracer is present during a scan, the resulting image represents the sum of all tracer present. As such, the images from separate, single-tracer PET scans can be added together to create “synthesized” multi-tracer PET images. Aside from small differences in scanner deadtime and random coincidence rates (which are well-understood and accurately corrected by the PET scanner), such synthesized dual-tracer images accurately mimic actual multi-tracer PET images, which characteristics that closely match what would have been obtained from actual multi-tracer scanning.

The advantage of this approach is that the actual single-tracer components of the resulting dual-tracer images are known exactly — and they can be used to evaluate the accuracy of individual-tracer images recovered from the multi-tracer images. In effect, the data become their own controls when using this approach.

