6.2. Dual- vs. Single-Tracer Performance Assessments

The PET images for each tracer pair will be co-registered and combined to synthesize corresponding dual-tracer images. Dual-tracer processing algorithms, based on modeling differences in radioactive decay rates and kinetic distributions for each tracer, will be developed that take simultaneous dual-tracer PET images as input and out separate, recovered images of each individual tracer. The performance of the dual-tracer scanning approach and processing algorithms will be evaluated by comparing output images for each tracer to the corresponding original single-tracer images for that tracer. A number of analyses will be performed on these data.

In the following paragraphs, “recovered” is used to denote measures (image pixel values, SUVs) for individual-tracer images recovered from the dual-tracer images, and “true” is used to denote the corresponding value from the original constituent single-tracer image. This analysis evaluates how accurately the simultaneous dual-tracer imaging technique can recover individual images of each tracer, as compared to the images from conventional single-tracer scans.

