6.2.3. Quantitative Performance Targets

The following quantitative performance targets have been set in order to conclude that the new simultaneous dual-tracer techniques provide images of each tracer that are equivalent to images that would be obtained from separate, single-tracer scans of each tracer:

- (1) dual-vs.-single correlation coefficients ≥ 0.95 for both image voxels and lesion SUVs;

- (2) bias, as measured by the linear regression slope, to be within 5% of 1.0 ($0.95 \leq \text{slope} \leq 1.05$);
- (3) bias, as measured by the linear regression intercept, to be within 5% (of mean voxel or SUV value) of zero; and
- (4) tumor and background tissue SUVs for dual-tracer images within 0.05 of those for the separate-scan standard images (to 95% power).

These analyses will be repeated for all 3 tracer pairs.

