6.3. Justification of Sample Size

The following sample size calculations are based on testing the hypothesis that differences in SUV_{mean} for lesions and normal tissue regions in images recovered from dual-tracer scanning for each tracer are less than 5% different than those from the single-tracer “standard” images, using a 2 sided *t*-test with alpha = 0.05 and desired power = 0.95. We also assume a standard deviation of 10% for SUV_{mean} measurements (based on PET test-retest variability). This gives a required sample size of $N = 104$. Assuming 5-7 regions/lesions per subject, this gives 15-20 subjects needed to obtain the desired statistical power, which supports our design of 15-20 patients each for each study Arm.

The study design and data analysis techniques were reviewed and approved by the NIH study section for grant 2R44CA257522, and no issues or concerns were noted.

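### Section 6.2.3 concludes equivalence from scores on the study data, but nothing separates patients used to tune or choose algorithms and scan protocols from patients used for scoring

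*Combined protocol and SAP*

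**What the plan says.** Five parts of the combined protocol and SAP bear on this.

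- **Development and testing.** Section 1.0 states: "New algorithms for processing dual-tracer PET images will be developed and tested using these data". It describes the synthesized images as "enabling development and testing of various simultaneous dual-tracer processing algorithms", so more than one algorithm is in view. Section 2.1 sets the current grant phase the task to "evaluate how well these algorithms can recover individual-tracer images from simultaneous dual-tracer PET datasets".
- **Scan protocols.** Section 6.0 says: "The imaging data will be used to develop dual-tracer PET scanning protocols and new processing algorithms". Section 6.1 faults the alternative three-exam design because it would fix a single dual-tracer scan protocol, "rather than allowing for various scanning protocols to be studied and compared". Comparing protocols on these data is therefore intended.
- **Scoring.** Section 6.2: "The performance of the dual-tracer scanning approach and processing algorithms will be evaluated by comparing output images for each tracer", the comparator being the original single-tracer images.
- **Conclusion.** Section 6.2.3 sets numeric targets "in order to conclude that the new simultaneous dual-tracer techniques provide images of each tracer that are equivalent" to those from separate scans. The targets are correlation of at least 0.95, slope between 0.95 and 1.05, intercept within 5% of zero, and SUVs within 0.05. They apply to all three tracer pairs.
- **Sample size.** Section 6.3 takes N = 104 regions and continues: "Assuming 5-7 regions/lesions per subject, this gives 15-20 subjects needed to obtain the desired statistical power". It treats this as support for the planned arm sizes.

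The documents mention no training and test split, hold-out set, cross-validation, lock of algorithm or protocol before scoring, or rule for choosing among candidates.

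**The concern.** A processing algorithm has settings, and a developer with several algorithms and scan protocols must choose among them. If the true single-tracer images guide the settings or the choice, the winning combination is partly fitted to those patients. Its correlation, slope, intercept and SUV differences in the same patients will then tend to look better than they would in a patient who played no part in development.

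This matters because of section 6.2.3. A statement that the technique gives images equivalent to separate scans is naturally read as applying to patients not yet scanned. The targets are narrow, so even modest optimism could decide whether one is met.

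**Working it through.** **1. Is there any separation?** Setting the sections side by side:

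| Step | Section | Data used |
|---|---|---|
| Develop algorithms | 1.0, 6.0, 6.2 | the study images |
| Develop and compare scan protocols | 6.0, 6.1 | the study images |
| Score against true images | 6.2, 6.2.2 | the study images |
| Conclude equivalence | 6.2.3 | the scores above |

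No row is limited to a subset of patients.

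**2. Does the sample size reserve patients for development?** Inputs from section 6.3: difference 5%, SD 10%, two-sided alpha 0.05, power 0.95. The stated N is reproduced by the formula for two independent samples:

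n = 2 × (1.960 + 1.645)² / (5/10)² = 103.96 with unrounded quantiles, so 104.

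At 7 regions per patient, 104/7 = 14.9, so 15 patients. At 5 regions, 104/5 = 20.8, so 21 patients. The plan's 15 to 20 corresponds to 15 × 7 = 105 and 20 × 5 = 100 regions. Section 6.3 thus converts the required regions into whole arms and assigns no patient to development only. This supports the reading that the same patients serve both purposes, but does not prove it.

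**3. Do the numbers rule out a separate test set?** No. Recovered and true values come in pairs from the same region, so a one-sample calculation on the differences is also relevant. Assume that the SD of the differences is 10% and, as the plan does, that regions are independent:

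n = (10 × (1.960 + 1.645) / 5)² = 51.98, so 52 by the normal approximation and 54 by the t-test (power 0.950).

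54/7 = 7.7, so 8 patients; 54/5 = 10.8, so 11 patients. An arm of 15 would leave 15 − 11 = 4 to 15 − 8 = 7 patients for development, and the arm of 20 would leave 9 to 12.

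**4. How large is the optimism?** That depends on how many algorithms and protocols are compared, how many parameters are tuned to the true images, and how strongly the candidates' scores are correlated. The documents give none of these, so no figure is offered.

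**The case against.** The strongest reply is that this is a technology-development study with little to overfit. The primary objective in section 1.1 is to obtain suitable data. Section 1.0 says the study is not an NIH-defined clinical trial and the algorithms belong to no medical device. Section 6.2 bases the algorithms on differences in decay and kinetics, and the half-lives in section 2.2.3 are known constants. Section 2.2.6 reports earlier Phase I work. No section describes a model trained on data. Section 6.2.3 does not mention future patients. The detailed algorithm plan sits in the grant, which may define a partition.

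Much of this stands. It limits both the likely size of the effect and how firmly it can be asserted. It does not remove the equivalence conclusion or the intended comparison of several algorithms and protocols, and selection can create optimism even with physics-based models. No locked algorithm is carried over from Phase I. The own-controls argument in sections 1.0 and 6.1 supplies a known reference image; it does not separate choosing from scoring. Section 2.2.6 says the same algorithms can serve all three pairs, so developing in one arm and testing in another would be possible, but it is not planned.

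A reader might infer three stronger points that the documents do not support:

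- **That the plan states each patient is used for both purposes.** It says development and testing use these data; the patient-level overlap is inferred.
- **That the arms are too small for a hold-out.** This depends on the two-sample formula. On the paired calculation above, 54 regions suffice and a hold-out is feasible.
- **That the bias is large.** Nothing in the documents allows it to be sized.

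**Conclusion.** The point holds as a missing safeguard attached to an explicit conclusion. Followed as written, the plan allows algorithms and scan protocols to be tuned, compared and scored on the same patients, and then allows equivalence to be concluded. The resulting agreement can be optimistic for new patients, by an amount that cannot be computed and may be modest.

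This rests on two assumptions: that no partition is described in the grant, and that the true images guide at least some tuning or selection. The acquisition of data is unaffected, and the arithmetic behind N = 104 is sound for the formula used. Whether that formula suits paired, clustered regions is a separate question. This should be corrected before scoring begins.

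**What to change.** Add a paragraph to section 6.2, fixed before any scoring, stating that:

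- data-driven tuning and the choice of algorithm and scan protocol are carried out inside patient-level cross-validation, with all regions and both tracers of a patient held out together;
- only recovered images from held-out patients count toward the 6.2.3 targets, and in-sample results are reported as development results;
- if tuning or revision of the model is not confined to the folds, for example because the model structure is changed after all patients' images have been seen, the 6.2.3 targets are reported as development benchmarks and equivalence is not concluded.

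If the grant already defines a partition, section 6.2 should state it.

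**Cost.** No extra scans or patients are needed, every patient is still scored, and the text can be added after acquisition. The price is computing time (more if protocol selection must be repeated in every fold), slightly fewer patients for tuning in each fold, possibly less favourable figures, and possible loss of the equivalence wording. Cross-validation protects only the steps rerun inside the folds. Full protection against later revision would need a locked algorithm and unseen patients, which is not requested here.

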1.1. Primary Objective

The primary objective is to obtain PET/CT imaging data suitable for developing new simultaneous dual-tracer PET techniques and processing algorithms for dual-tracer imaging of FDG + Cu64-DOTATATE, FDG + Ga68-DOTATATE, and FDG + Ga68-PSMA-11 PET/CT.

1.2. Secondary Objective

The data obtained may also provide insight into the combined value of dual-tracer PET/CT images with these tracers. The secondary objective of the study is to preliminarily assess the combined value of dual-tracer images with these tracers as compared to single-tracer images. The relative uptake of each tracer in tumors will be assessed to determine the potential for improved detection sensitivity and specificity for dual-tracer imaging as compared to single-tracer imaging. This secondary objective is exploratory in nature, and may result in preliminary data suitable for designing subsequent hypothesis-driven research studies in this area.

2.0 BACKGROUND

2.1. Dual-Tracer PET Technologies and MFI

MultiFunctional Imaging LLC (MFI) is a University of Utah spinoff company that is investigating technologies patented at the University for rapidly imaging multiple PET tracers in a single scan. Under research grant 2R44CA257522, MFI is investigating novel techniques for simultaneously imaging several tracer pairs. These include simultaneous imaging of FDG + Cu64-DOTATATE and FDG+ Ga68-DOTATATE for NETs, and of FDG + Ga68-PSMA for prostate cancer. The rationale for imaging these tracer combinations is provided below. The proof-of-concept for the new simultaneous dual-tracer PET techniques was established under a previous Phase I grant. The current Phase II grant will study the new simultaneous dual-tracer PET techniques in depth,

develop new algorithms for processing simultaneous dual-tracer PET images, and evaluate how well these algorithms can recover individual-tracer images from simultaneous dual-tracer PET datasets.

The clinical research study described by this protocol is designed to obtain dual-tracer PET/CT imaging data with each tracer pair according to the Specific Aims of the grant, providing the imaging data needed to develop new simultaneous dual-tracer imaging techniques and processing algorithms for these tracer pairs. The study design uses established physics/engineering principles, and it is based on two decades of research and development in dual-tracer PET by the investigators.

